## **IV. Risk/Benefit Assessment**

### **1. Benefits (Individual and Societal Benefits)**

This study intends to explore the impact of nebulized Sapylin inhalation on the therapeutic efficacy of CCRT in patients with NPC via nebulized inhalation, observe the effect of nebulized Sapylin inhalation on the incidence and severity of RIOM, and evaluate the safety of nebulized Sapylin inhalation. This study aims to find a highly efficient and low-toxicity method for NPC specialists and patients to reduce the occurrence and severity of RIOM and improve the efficacy of CCRT.

### **2. Risks**

- (1) Efficacy and adverse reaction risks;
- (2) Time risk;
- (3) Policy risk;
- (4) Personnel risk.

Mitigation Measures: Flexibility (high variability); diverse services; low cost; shortened research time; expanded research resources; and the ability to adapt to and meet strict GCP requirements, etc.

### **3. Protection of Special Populations (Women, children, the elderly, and other special populations such as incarcerated individuals, etc., risk and protection)**

The study population for this project consists of NPC patients aged 18-75. The research personnel will conduct risk assessment for women, the elderly, and other special populations, and implement corresponding risk protection measures.

## **V. Ethical Issues in the Study**

### **1. Ethics Approval**

This clinical trial has followed the Declaration of Helsinki and China's relevant clinical trial research norms and regulations. The implementation of this trial protocol has been approved by the Ethics Committee of the principal clinical research unit prior to the start of the trial.

### **2. Informed Consent**

Before any patient is selected for this study, the investigator must fully and comprehensively introduce the study's objectives, procedures, and possible risks to the patient's family members or their designated representatives in written form. Patients and their family members should be informed that they have the right to withdraw from the study at any time. A written Patient

Informed Consent Form (included as an appendix to the protocol) must be provided to every patient and family member before enrollment. The investigator must obtain informed consent before any patient or family member enters the study, and the informed consent form must be retained as a clinical trial document for inspection.

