### **3.3 Inclusion and Exclusion Criteria and Sample Size Estimation**

(1) Patient Selection: Meeting the diagnostic criteria for NPC; patients who have not yet received concurrent chemoradiotherapy; meeting the case inclusion and exclusion criteria; patients voluntarily joining this clinical trial and signing the informed consent form.

(2) Sample Size Estimation: The Delphi method is used to determine the non-inferiority margin of the observation endpoint. After consulting senior oncology practitioners, we defined an 8% reduction in the incidence of RIOM as a clinically acceptable non-margin of error. Under the conditions of test level  $\alpha=0.05$  and test efficacy  $1-\beta=0.9$ , the proportion of cases in the two groups is 1:1. Using the module of non-destructiveness Tests for Two Proportions in PASS 15.0 statistical analysis software, we determined that a sample size of 81 was required per group. Considering a 10% loss to follow-up rate, we estimated that 90 cases would be required in each group, for a total of 180 cases.

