### **III. Study Participant Recruitment**

#### **1. Inclusion Criteria**

- (1) stage III-IVa NPC (AJCC 8th edition) diagnosed via pathology in a tertiary hospital;
- (2) no previous radiotherapy, chemotherapy, surgery, immunization, or targeted therapy;
- (3) Karnofsky Performance Status score  $\geq 80$ ;
- (4) intact and normal oral mucosa before treatment;
- (5) age 18–75 years;
- (6) voluntary participation and provision of informed consent in person;
- (7) routine blood examination: white blood cell count  $\geq 4.0 \times 10^9/L$ , hemoglobin  $\geq 100g/L$ , neutrophil count  $\geq 1.5 \times 10^9/L$ , and platelet count  $\geq 100 \times 10^9/L$ ;
- (8) biochemical examination: total bilirubin  $\leq 1.5 \times$  the upper limit of the normal range (ULN), alanine aminotransferase and aspartate aminotransferase  $\leq 2 \times$  ULN, and estimated glomerular filtration rate  $\geq 60$  mL/min.

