#### **2. Exclusion Criteria**

- (1) with other malignant tumors in the past or present and/or distant metastasis during treatment;
- (2) who have undergone surgery, chemoradiotherapy, and targeted immunotherapy;
- (3) with a history of asthma, rash, urticaria, and other allergic diseases;
- (4) with a history of autoimmune diseases, connective tissue diseases, and diabetes mellitus that significantly affect the healing of the oral mucosa;
- (5) with concomitant diseases, such as heart disease, kidney disease, and acute infectious diseases, which are judged by the investigator to seriously endanger the safety of patients or affect the completion of the study;
- (6) who are breastfeeding, pregnant, or planning to become pregnant during the study;
- (7) with known allergies to the therapeutic agents and penicillin used in the trial;
- (8) with mental or nervous system diseases or poor compliance will be excluded from the study.

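### The consent section owes the full explanation of aims, procedures and risks to relatives or representatives and does not name the adult patient, who must consent and sign in person

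*Protocol*

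**What the plan says.** Protocol V.2 (Informed Consent) contains one sentence that imposes a duty to explain the study. The investigator must, in full, "introduce the study's objectives, procedures, and possible risks to the patient's family members or their designated representatives in written form".

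The rest of V.2 does mention the patient:

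- On withdrawal: "Patients and their family members should be informed that they have the right to withdraw from the study at any time".
- On the document itself, the written Patient "Informed Consent Form (included as an appendix to the protocol) must be provided to every patient and family member before enrollment".
- On consent: "The investigator must obtain informed consent before any patient or family member enters the study".

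The eligibility and recruitment sections address the patient alone. Inclusion criterion (6) in III.1 requires "voluntary participation and provision of informed consent in person". Section II.3.3 describes "patients voluntarily joining this clinical trial and signing the informed consent form", and III.5 repeats this. Criterion (5) in III.1 sets "age 18–75 years", and exclusion (8) in III.2 removes those "with mental or nervous system diseases or poor compliance will be excluded from the study".

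**The concern.** The duty to explain is the core of a consent procedure, and V.2 gives that duty a recipient other than the participant. Relatives or representatives become the default audience for the explanation of every enrolment, with no condition attached, although the protocol never says when a representative would be needed. The closing sentence adds to the confusion: family members do not enter this trial, so its mention of them leaves it unclear whose consent is meant.

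What is at stake is first the patient's position. The experimental treatment is a bacterial preparation nebulised once daily through radiotherapy, in a use that the background section calls rarely reported in this disease. The person inhaling it should be the one to whom its risks are explained.

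There is also a smaller consequence for trial conduct. If the loose wording ever led to a form signed by a relative in place of the patient, that patient would fail inclusion criterion (6). III.3.4 lists failure of the inclusion criteria as a ground for excluding a case, so the problem would surface after randomisation.

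**Working it through.** No arithmetic applies, and the protocol gives no figure to reproduce. The check is to set the sections side by side and ask, for each step of consent, who is named.

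| Step | Section | Person named |
|---|---|---|
| Objectives, procedures and risks explained | V.2 | Family members or designated representatives |
| Right to withdraw explained | V.2 | Patients and family members |
| Written form provided before enrolment | V.2 | Every patient and family member |
| Consent obtained before entry | V.2 | Any patient or family member |
| Consent given in person | III.1 (6) | The participant |
| Form signed | II.3.3 and III.5 | The patient |

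Four things follow.

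1. **The omission is confined to the first row.** The two sentences that follow it in V.2 name both patients and family. The drafting can therefore name both when it intends to, and the explanation sentence is hard to read as shorthand for both.

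2. **The fourth row conflicts with the last two.** Consent that might come from a patient or a family member does not match consent given in person by a patient who signs.

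3. **Eligibility supplies no reason for the difference.** Participants are 18 to 75 with a Karnofsky score of at least 80, and mental or nervous system disease is an exclusion. These criteria do not prove that no patient could ever need help, for example with reading the form. But the protocol states no ground for a representative and no procedure for one. Section IV.3 promises a risk assessment for women, the elderly and other special populations, and does not mention proxy consent.

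4. **The third row and the last two limit the damage.** The patient must be handed the form before enrolment and must sign it. Whoever follows all the sections cannot properly enrol a patient who has received nothing. What remains possible is narrower: a relative has the full discussion of risks, the patient receives and signs the form, and V.2 has been followed to the letter.

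**The case against.** The strongest reply is that the sections must be read together. The same centre that follows V.2 is bound by II.3.3, III.1 and III.5, and V.2 itself puts the written form in every patient's hands before enrolment. A consent form is the usual place for objectives, procedures and risks. The protocol says that it is an appendix, and it is not part of the text available here. On this view V.2 contains a drafting slip in a document that has others, such as the garbled terms in the sample size paragraph.

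Much of this stands, and it rules out several stronger readings that a reader might infer:

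- **That patients could be enrolled without being told the risks.** V.2 requires that they receive the form, and the form's content cannot be checked here, so it cannot be assumed to be silent on risk.
- **That a relative may sign for the patient.** No sentence authorises this. The phrase about a family member entering the study is loose and does not amount to a proxy rule.
- **That a briefing given only to a relative is an eligibility violation.** Criterion (6) concerns voluntary participation and consent in person. It does not say who was briefed. A patient who then signs in person still meets its wording, and III.3.4 is not triggered.
- **That all 180 planned patients are affected.** That figure is the sample size. Nothing in the protocol shows how anyone was in fact briefed or who signed.
- **That allergy or asthma histories would be missed.** These are exclusion criteria to be checked when eligibility is assessed, and they do not depend on who heard the explanation of risks.

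What the reply does not answer is the sentence itself. Being given a form is less than the full explanation that V.2 requires for relatives, and no other section extends that explanation to the patient.

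**Conclusion.** The point holds as an internal inconsistency in an operative rule. V.2 addresses the duty to explain to the wrong person and speaks loosely of whose consent is obtained, while II.3.3, III.1 (6) and III.5 place consent and signature with the adult patient. The full explanation is therefore not expressly owed to the person who takes on the risk.

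The size is modest. Nothing in the estimand, sample size, randomisation or analysis changes, and no count of affected patients can be given. Loss of a case under III.3.4 would arise only if a form were found without the patient's own signature, and the protocol gives no sign that this has happened.

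The conclusion rests on the consent wording in the protocol as it stands. It makes no assumption about the content of the consent form or about practice on the ward. It is still worth correcting, because the section is meant to protect every participant and the correction is plain.

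**What to change.** Make two changes in V.2:

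1. In the explanation sentence, name the patient as the person to whom objectives, procedures and possible risks are explained, and add that family members may attend.
2. In the last sentence, replace the reference to any patient or family member with wording to this effect: the patient personally gives and signs consent before entering the study, in line with inclusion criterion (6).

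Alongside this, make a routine check that the forms on file carry the patient's own signature. Renewed consent is needed only where a form is found without it.

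The cost is a short wording amendment and a file check. No design, sample size or analysis text has to change.

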## VI. Annual Plan

Study Period	Key Responsibilities
Jul 2022 - Jun 2024	
 
1. Initiate recruitment;
 
2. Screen eligible NPC cases, determine baseline data and collect indicators, perform randomization, and complete the enrollment of the expected sample size; it is planned to recruit 90 patients in the 2 years (45 in the experimental group, 45 in the control group) and conduct follow-up observations on these subjects;
 
3. Follow up each enrolled case for 1 year;
 
4. The enrolled cases will proceed according to the trial steps designed for each group, including patient follow-up, disease assessment, and indicator collection and follow-up.
 

Jul 2024 - Jun 2026	
 
1. Screen eligible NPC cases, determine baseline data and collect indicators, perform randomization, and complete the enrollment of the expected sample size; it is planned to recruit 90 patients in the second 2 years period (45 in the experimental group, 45 in the control group);
 
2. Follow up each enrolled case for 1 year, and perform data registration and statistics;
 
3. The enrolled cases will proceed according to the trial steps designed for each group, including patient follow-up, disease assessment, and indicator collection and follow-up.
 

Jul 2026 - Jul 2027	
 
1. Statistical analysis, thesis writing, domestic and international exchange, and promotion application.
 

## VII. Assessment Indicators

The primary assessment indicator is the incidence and severity of RIOM. The secondary assessment indicators are: (1) duration of RIOM, (2) rate of completion of treatment measures, (3) adverse events classified according to CTCAE 5.0, and (4) changes in BMI.

## VIII. Preliminary Research Foundation and Working Conditions

The research team conducted a retrospective study on 32 NPC (NPC) patients from 2016 to 2019. The study observed the effect of nebulized Sapylin and Dexamethasone on the incidence rate of RIOM (radiation-induced oral mucositis) and the efficacy of CCRT (Concurrent

Chemoradiotherapy) during concurrent chemoradiotherapy. Results showed: The CCRT combined with nebulized Sapylin group had a lower incidence rate of RIOM and Grade III-IV RIOM compared to the CCRT combined with nebulized Dexamethasone group (43.75% vs 68.75%) and (12.5% vs ≥31.3%), respectively. Furthermore, the CCRT combined with nebulized Sapylin group was superior to the CCRT combined with nebulized Dexamethasone group in terms of objective response rate (ORR) (87.5% vs 62.5%), median overall survival (OS) (53.7M vs 46.4M), and median progression-free survival (PFS) (27M vs 23M). Moreover, comparison of the efficacy and survival analysis between the CCRT combined with nebulized Sapylin group and the CCRT combined with nebulized Dexamethasone group revealed that the nebulized Sapylin inhalation group showed a trend toward reducing the incidence rate of Grade III-IV RIOM and enhancing CCRT efficacy in NPC patients, with no obvious toxic side effects observed. Therefore, this project will conduct a non-inferiority, parallel-design, randomized controlled study of nebulized Sapylin versus nebulized Dexamethasone for the prevention and treatment of radiation-induced oral mucositis in NPC.

#### (I) Research Methods

##### 1. Study Subjects

Data of NPC patients with complete clinical and pathological data who underwent concurrent chemoradiotherapy at the Head and Neck Tumor Ward of the Cancer Hospital of the Affiliated Hospital of Guangdong Medical University between May 2016 and December 2019 were observed.

###### 1.1 Inclusion Criteria:

- (1) stage III-IVa NPC (AJCC 8th edition) diagnosed via pathology in a tertiary hospital;
- (2) no previous radiotherapy, chemotherapy, surgery, immunization, or targeted therapy;
- (3) Karnofsky Performance Status score ≥80;
- (4) intact and normal oral mucosa before treatment;
- (5) age 18–75 years;
- (6) voluntary participation and provision of informed consent in person;
- (7) routine blood examination: white blood cell count  $\geq 4.0 \times 10^9/L$ , hemoglobin  $\geq 100g/L$ , neutrophil count  $\geq 1.5 \times 10^9/L$ , and platelet count  $\geq 100 \times 10^9/L$ ;
- (8) biochemical examination: total bilirubin  $\leq 1.5 \times$  the upper limit of the normal range (ULN), alanine aminotransferase and aspartate aminotransferase  $\leq 2 \times$  ULN, and estimated glomerular filtration rate  $\geq 60$  mL/min.

###### 1.2 Exclusion Criteria

- (1) with other malignant tumors in the past or present and/or distant metastasis during treatment;
- (2) who have undergone surgery, chemoradiotherapy, and targeted immunotherapy;
- (3) with a history of asthma, rash, urticaria, and other allergic diseases;
- (4) with a history of autoimmune diseases, connective tissue diseases, and diabetes mellitus that significantly affect the healing of the oral mucosa;
- (5) with concomitant diseases, such as heart disease, kidney disease, and acute infectious diseases, which are judged by the investigator to seriously endanger the safety of patients or affect the completion of the study;
- (6) who are breastfeeding, pregnant, or planning to become pregnant during the study;
- (7) with known allergies to the therapeutic agents and penicillin used in the trial;
- (8) with mental or nervous system diseases or poor compliance will be excluded from the study.

##### 2. Treatment Methods: NPC patients will undergo CCRT, divided into the CCRT combined with nebulized Sapylin group and the CCRT combined with nebulized Dexamethasone group.

###### 2.1 CCRT combined with nebulized Sapylin group:

Concurrent Radiotherapy Dose: Nasopharyngeal primary tumor site (PTVnx): 69.96Gy/2.12Gy/33F; High-risk planning target volume (PTV1): 60.06Gy/1.82Gy/33F; Low-risk planning target volume (PTV2): 54.12Gy/1.64Gy/33F; Cervical lymph nodes (PTVnd): 66 ~ 69.96Gy/2 ~ 2.12Gy/33F; 5 times per week, for a total of 6-7 weeks.

Concurrent Chemotherapy: Cisplatin (80-100mg/m^2, Q3W, 3 times during CCRT); Sapylin: 1 KE/time, nebulized, QD, starting from Day 1 of CCRT until the end of radiotherapy.

###### 2.2 CCRT combined with nebulized Dexamethasone group:

Concurrent Radiotherapy Dose: Nasopharyngeal primary tumor site (PTVnx):

69.96Gy/2.12Gy/33F; High-risk planning target volume (PTV1): 60.06Gy/1.82Gy/33F; Low-risk planning target volume (PTV2): 54.12Gy/1.64Gy/33F; Cervical lymph nodes (PTVnd): 66 ~ 69.96Gy/2 ~ 2.12Gy/33F; 5 times per week, for a total of 6-7 weeks.

Concurrent Chemotherapy: Cisplatin (80-100mg/m^2, Q3W, 3 times during CCRT); Dexamethasone: 10mg/time, nebulized, QD, starting from Day 1 of treatment until the end of radiotherapy.

3. Observation Indicators: The primary observation indicator is the RIOM incidence rate. The secondary observation indicators are: Grade III-IV RIOM incidence rate; RIOM onset time and duration; assessment of adverse reactions, ORR, and PFS for both regimens.

#### 4. Statistical Methods

① General Principles: One-sided tests will be used for superiority tests, while two-sided tests will be used for other statistical tests. Quantitative indicators will be described using the number of cases, mean, standard deviation, median, minimum, and maximum. Categorical indicators will be described using the number of cases and percentages. All statistical analyses will be conducted using SPSS 26.0 statistical software.

##### ② Statistical Analysis Populations:

**Full Analysis Set (FAS):** Refers to the ideal set of subjects that closely adheres to the intention-to-treat principle. It includes all randomized subjects who have received at least one treatment. The number of subjects evaluated for efficacy at the endpoint in each group will remain consistent with the number at the start of the trial.

**Per Protocol Set (PPS):** Includes all cases that comply with the trial treatment protocol, have good compliance (used the trial drug quantity between 80% and 120%), completed the required fields in the CRF, have measurable primary variables, have no missing baseline variables, and have no major violations of the trial protocol.

**Safety Analysis Set (SS):** Includes all enrolled cases that have used the study medication at least once and have safety records after drug administration. This data set is used for safety analysis.

In this trial, baseline data will be analyzed using the FAS. Primary efficacy endpoints will be analyzed simultaneously on the FAS and PPS. Safety evaluation will be conducted using the SS.

#### (II) Preliminary Research Work

##### 1. Clinical and Pathological Features of NPC Patients Receiving Chemotherapy:

A retrospective study reviewed 32 NPC patients with complete clinical and pathological data who underwent concurrent chemoradiotherapy at the Head and Neck Tumor Ward of the Cancer Hospital of the Affiliated Hospital of Guangdong Medical University between May 2016 and December 2019. NPC patients were predominantly male (63.8%), with an average age of 51±15 years. The pathological types of NPC were mainly undifferentiated non-keratinizing carcinoma (90.2%) and differentiated non-keratinizing carcinoma (6.35%). The vast majority of NPC patients were TNM stage III-IVa.

##### 2. Observation of treatment efficacy, prognosis, RIOM incidence, and severity in NPC patients:

*Table 1 Efficacy and Survival Analysis of CCRT combined with Nebulized Sapylin Group versus CCRT combined with Nebulized Dexamethasone Group in the Treatment of Locally Advanced NPC*

Group	N	PR+CR	PD	Median OS (months)	Median PFS (months)
CCRT + Sapylin Neb.	16	14	1	53.7M	27M
CCRT + Dexamethasone Neb.	16	0	3	46.4M	23M

CCRT: Concurrent Chemoradiotherapy 、 PR: Partial Remission/Response 、 CR: Complete Remission/Response 、 PD: Progressive Disease 、 OS: Overall Survival 、 PFS: Progression-Free Survival

[figure not shown]

Figure 1 Survival Analysis of CCRT combined with Nebulized Sapylin Group versus CCRT combined with Nebulized Dexamethasone Group in the Treatment of Locally Advanced NPC.

Table 2 Grading of Toxic/Adverse Reactions (CTCAE Version 5) in CCRT combined with Nebulized Sapylin Group versus CCRT combined with Nebulized Dexamethasone Group in the Treatment of Locally Advanced NPC.

Adverse Event	CCRT + Sapylin Neb.					CCRT + Dexamethasone Neb.				
	0	I	II	III	IV	0	I	II	III	IV
Anemia	2	4	7	3	0	1	3	7	5	0
White blood cell decreased	4	4	6	2	0	4	3	5	4	0
Neutrophil count decreased	16	0	0	0	0	12	0	4	0	0
Platelet count decreased	15	0	1	0	0	12	2	1	1	0
Weight loss	0	8	8	0	0	1	6	6	3	0
Vomiting	5	6	5	0	0	2	4	6	3	1
Nausea	5	8	3	0	0	3	5	5	3	0
RIOM	9	1	4	2	0	5	2	4	3	2

The results from Table 1 show that the treatment response rate in the CCRT combined with nebulized Sapylin inhalation group was higher than in the Dexamethasone group, suggesting that nebulized Sapylin inhalation can improve the efficacy of CCRT and prolong patient OS. The results from Table 2 show that a comparison of common adverse reactions between the two groups suggests that the CCRT combined with nebulized Sapylin inhalation group can reduce the incidence and severity of RIOM, and can reduce overall adverse reactions.

